15.3 Subject Confidentiality

The sponsor and designees affirm and uphold the principle of the subject's right to protection against invasion of privacy. Throughout this study, a subject's source data will only be linked to the sponsor's clinical trial database or documentation via a subject identification number. As permitted by all applicable laws and regulations, limited subject attributes, such as sex, age, or date of birth, and subject initials may be used to verify the subject and accuracy of the subject's unique identification number.

To comply with ICH Guidelines for GCP and to verify compliance with this protocol, the sponsor requires the investigator to permit the monitor or the sponsor's designee, representatives from any regulatory authority (eg, Ministry of Health of Russian Federation, Food and Drug Administration, Medicines and Healthcare products Regulatory Agency, Pharmaceuticals and Medical Devices Agency), the sponsor's designated auditors, and the appropriate IRBs and IECs to review the subject's original medical records (source data or documents), including, but not limited to, laboratory test result reports, ECG reports, admission and discharge summaries for hospital admissions occurring during a subject's study participation, and autopsy reports. Access to a subject's original medical records requires the specific authorization of the subject as part of the informed consent process (see Section 15.2).

Copies of any subject source documents that are provided to the sponsor must have certain personally identifiable information removed (ie, subject name, address, and other identifier fields not collected on the subject's eCRF).

15.4 Publication, Disclosure, and Clinical Trial Registration Policy

15.4.1 Publication and Disclosure

The investigator is obliged to provide the sponsor with complete test results and all data derived by the investigator from the study. During and after the study, only the sponsor may make study information available to other study investigators or to regulatory agencies, except as required by law or regulation. Except as otherwise allowable in the study site agreement, any public disclosure (including publicly accessible websites) related to the protocol or study results, other than study recruitment materials and/or advertisements, is the sole responsibility of the sponsor.

The sponsor may publish any data and information from the study (including data and information generated by the investigator) without the consent of the investigator. Manuscript authorship for any peer-reviewed publication will appropriately reflect contributions to the production and review of the document. All publications and presentations must be prepared in accordance with this section and the study site agreement. In the event of any discrepancy between the protocol and the study site agreement, the study site agreement will prevail.

The investigator needs to obtain a prior written approval from the sponsor to publish any information from the study externally such as to a professional association.

15.4.2 Clinical Trial Registration

In order to ensure that information on clinical trials reaches the public in a timely manner and to comply with applicable laws, regulations and guidance, Takeda will, at a minimum register all interventional clinical trials it sponsors anywhere in the world on ClinicalTrials.gov and/or other publicly accessible websites before start of study, as defined in Takeda Policy/Standard. Takeda contact information, along with investigator's city, state (for America), country, and recruiting status will be registered and available for public viewing.

For some registries, Takeda will assist callers in locating study sites closest to their homes by providing the investigator name, address, and phone number to the callers requesting trial information. Once subjects receive investigator contact information, they may call the site requesting enrollment into the trial. The investigative sites are encouraged to handle the trial inquiries according to their established subject screening process. If the caller asks additional questions beyond the topic of trial enrollment, they should be referred to the sponsor.

Any investigator who objects to the sponsor providing this information to callers must provide the sponsor with a written notice requesting that their information not be listed on the registry site.

15.4.3 Clinical Trial Results Disclosure

Takeda will post the results of clinical trials on ClinicalTrials.gov or other publicly accessible websites, as required by Takeda Policy/Standard, applicable laws and/or regulations.

15.5 Insurance and Compensation for Injury

Each subject in the study must be insured in accordance with the regulations applicable to the site where the subject is participating. If a local underwriter is required, then the sponsor or sponsor's designee will obtain clinical study insurance against the risk of injury to study subjects. Refer to the study site agreement regarding the sponsor's policy on subject compensation and treatment for injury. If the investigator has questions regarding this policy, he or she should contact the sponsor or sponsor's designee.

Subjects will be provided with their individual insurance policy. Takeda has insured subjects with the following insurance company:

«INGOSSTRAKH» Insurance Company ([name])

Appendix A Schedule of Study Procedures

Study Day:	Days -28 to -2 (b)	Drug Intake Periods 1 through 4 (a)					Study Exit (Day 4 of Period 4)/ Early Termination Visit	Follow-up Phone Call (d)
		Day -1 (Check-in)	Day 1 (c)	Day 2	Day 3	Day 4 (Periods 1, 2, and 3)		
Informed consent	X							
Inclusion/exclusion criteria	X	X						
Demographics and medical history	X							
Medication history	X							
Physical examination	X	X					X	
Vital signs (e)	X	X	X			X	X	
Height, weight and BMI	X							
Concomitant medications	X	X	X	X	X	X	X	X
12-lead ECG (f)	X	X					X	
Clinical laboratory evaluations (g)	X		X (h)				X	
Urine drug, cotinine, and alcohol breath screen	X	X			X	X	X	
Urine pregnancy test (hCG) (i)	X	X					X	
HBsAg, Anti-HCV, HIV, and syphilis (i)	X							
Confinement		X	X (j)	X (j)				
Study drug dosing (k)			X					
PK blood collection (l)			X	X	X	X	X	
Predose/AE assessment (m)	X	X	X	X	X	X	X	X

Footnotes are on the following page.

CONFIDENTIAL

- (a) There will be at least 7 days between the dose in 1 period and the dose in a subsequent period.
- (b) Screening may consist of 1 or more visits. Subjects will sign an informed consent form at the first visit and return to the clinic in a fasted state for safety laboratory testing at the second visit. Screening procedures must be performed within 28 days prior to administration of investigational product.
- (c) Day 1 of each drug intake period.
- (d) Follow-up phone call will be made 14 ± 2 days after study exit to inquire about any AE or SAEs, and concomitant medications taken since final dose. Any AE/SAE spontaneously reported within 30 days postdose will be included within the database as AEs.
- (e) Vital signs: oral body temperature, sitting blood pressure (after resting 5 minutes), respiratory rate, and pulse (beats per minute). Vital signs will be measured just prior to dosing on Day 1 of periods 1 through 4. When vital signs are scheduled at the same time as blood draws, the blood draw will take priority and vital signs will be obtained within 0.5 hour before or after the scheduled blood draw.
- (f) ECG performed at Screening, Check-in (Day -1 of Period 1), and Study Exit Day 4 of Period 4, or if a subject terminates early from the study.
- (g) Hematology, serum chemistries, and urinalysis tests will be done at a local laboratory.
- (h) Predose hematology, serum chemistries, and urinalysis tests will be done for Period 1 only.
- (i) A urine pregnancy test and HBsAg, Anti-HCV, HIV, and syphilis tests will be done locally.
- (j) Following the 24-hour blood sample collection on Day 2 of each period, subjects will be discharged from the clinic and will return to the clinic for the 36-hour blood sample collection on Day 2 and on Days 3 and 4 of each period to complete study procedures.
- (k) Study drug will be administered on Day 1 of each period at 08:00 (± 1) hours, following an 8- hour fast. Dosing may be staggered to help facilitate logistics at the site.
- (l) Blood samples for PK obtained predose (within 15 minutes prior to dose), 0.25, 0.5, 1, 1.5, 2, 3, 4, 6, 8, 12, 16, 24, 36, 48, and 72 hours postdose. The PK sample should not be collected at the Early Termination Visit if a PK collection is not scheduled.
- (m) Predose AEs will be captured immediately following the signing of the informed consent at Screening until dosing on Day 1 of Period 1. The routine collection of AEs will continue through to the follow-up phone call.

Appendix B Responsibilities of the Investigator

Clinical research studies sponsored by the sponsor are subject to ICH GCP and all the applicable local laws and regulations.

The investigator agrees to assume the following responsibilities:

1. Conduct the study in accordance with the protocol.
2. Personally conduct or supervise the staff who will assist in the protocol.
3. If the investigator/institution retains the services of any individual or party to perform trial-related duties and functions, the investigator/institution should ensure that this individual or party is qualified to perform those trial-related duties and functions and should implement procedures to ensure the integrity of the trial-related duties and functions performed and any data generated.
4. Ensure that study related procedures, including study specific (non-routine/non-standard panel) screening assessments, are NOT performed on potential subjects, prior to the receipt of written approval from relevant governing bodies/authorities.
5. Ensure that all colleagues and employees assisting in the conduct of the study are informed of these obligations.
6. Secure prior approval of the study and any changes by an appropriate IRB/IEC that conform to ICH and local regulatory requirements.
7. Ensure that the IRB/IEC will be responsible for initial review, continuing review, and approval of the protocol. Promptly report to the IRB/IEC all changes in research activity and all anticipated risks to subjects. Make at least yearly reports on the progress of the study to the IRB/IEC, and issue a final report within 3 months of study completion.
8. Ensure that requirements for informed consent, as outlined in ICH and local regulations, are met.
9. Obtain valid informed consent from each subject who participates in the study, and document the date of consent in the subject's medical chart. Valid informed consent is the most current version approved by the IRB/IEC. Each informed consent form should contain a subject authorization section that describes the uses and disclosures of a subject's personal information (including personal health information) that will take place in connection with the study. If an informed consent form does not include such a subject authorization, then the investigator must obtain a separate subject authorization form from each subject.
10. Prepare and maintain adequate case histories of all persons entered into the study, including eCRFs, hospital records, laboratory results, etc, and maintain these data for a minimum of 2 years following notification by the sponsor that all investigations have been discontinued or that the regulatory authority has approved the marketing application. The investigator should contact and receive written approval from the sponsor before disposing of any such documents.

11. Allow possible inspection and copying by the regulatory authority of GCP-specified essential documents.
12. Maintain current records of the receipt, administration, and disposition of sponsor-supplied drugs, and return all unused sponsor-supplied drugs to the sponsor.
13. Report adverse reactions to the sponsor promptly. In the event of an SAE, notify the sponsor within 24 hours.

Appendix C Elements of the Subject Informed Consent

In seeking informed consent, the following information shall be provided to each subject:

1. A statement that the study involves research.
2. An explanation of the purposes of the research.
3. The expected duration of the subject's participation.
4. A description of the procedures to be followed, including invasive procedures.
5. The identification of any procedures that are experimental.
6. The estimated number of subjects involved in the study.
7. A description of the subject's responsibilities.
8. A description of the conduct of the study.
9. A statement describing the treatment(s) and the probability for random assignment to each treatment.
10. A description of the possible side effects of the treatment that the subject may receive.
11. A description of any reasonably foreseeable risks or discomforts to the subject and, when applicable, to an embryo, fetus, or nursing infant.
12. A description of any benefits to the subject or to others that reasonably may be expected from the research. When there is no intended clinical benefit to the subject, the subject should be made aware of this.
13. Disclosures of appropriate alternative procedures or courses of treatment, if any, that might be advantageous to the subject and their important potential risks and benefits.
14. A statement describing the extent to which confidentiality of records identifying the subject will be maintained, and a note of the possibility that regulatory agencies, auditor(s), IRB/IEC, and the monitor may inspect the records. By signing a written informed consent form, the subject is authorizing such access.
15. For research involving more than minimal risk, an explanation as to whether any compensation and an explanation as to whether any medical treatments are available if injury occurs and, if so, what they consist of or where further information may be obtained.
16. The anticipated prorated payment(s), if any, to the subject for participating in the study.
17. The anticipated expenses, if any, to the subject for participating in the study.
18. An explanation of whom to contact for answers to pertinent questions about the research (investigator), subject's rights, and IRB/IEC and whom to contact in the event of a research-related injury to the subject.
19. A statement that participation is voluntary, that refusal to participate will involve no penalty or loss of benefits to which the subject otherwise is entitled, and that the subject may discontinue

participation at any time without penalty or loss of benefits to which the subject is otherwise entitled.

20. The consequences of a subject's decision to withdraw from the research and procedures for orderly termination of participation by the subject.
21. A statement that the subject will be informed in a timely manner if information becomes available that may be relevant to the subject's willingness to continue participation in the study.
22. The foreseeable circumstances or reasons under which the subject's participation in the study may be terminated.
23. A written subject authorization (either contained within the informed consent form or provided as a separate document) describing to the subject the contemplated and permissible uses and disclosures of the subject's personal information (including personal health information) for purposes of conducting the study. The subject authorization must contain the following statements regarding the uses and disclosures of the subject's personal information:
 - a) that personal information (including personal health information) may be processed by or transferred to other parties in other countries for clinical research and safety reporting purposes, including, without limitation, to the following: (1) Takeda, its affiliates, and licensing partners; (2) business partners assisting Takeda, its affiliates, and licensing partners; (3) regulatory agencies and other health authorities; and (4) IRBs/IECs;
 - b) it is possible that personal information (including personal health information) may be processed and transferred to countries that do not have data protection laws that offer subjects the same level of protection as the data protection laws within this country; however, Takeda will make every effort to keep your personal information confidential, and your name will not be disclosed outside the clinic unless required by law;
 - c) that personal information (including personal health information) may be added to Takeda's research databases for purposes of developing a better understanding of the safety and effectiveness of the study drug(s), studying other therapies for patients, developing a better understanding of disease, and improving the efficiency of future clinical studies;
 - d) that subjects agree not to restrict the use and disclosure of their personal information (including personal health information) upon withdrawal from the study to the extent that the restricted use or disclosure of such information may impact the scientific integrity of the research; and
 - e) that the subject's identity will remain confidential in the event that study results are published.
24. Female subjects of childbearing potential (eg, nonsterilized, premenopausal female subjects) who are sexually active must use highly effective contraception (as defined in the informed consent) from Screening and throughout the duration of the study, and for 35 days after the last dose of study drug. Regular pregnancy tests will be performed throughout the study for all

female subjects of childbearing potential. If a subject is found to be pregnant during study, study drug will be discontinued and the investigator will offer the subject the choice to receive unblinded treatment information.

25. A statement that clinical trial information from this trial will be publicly disclosed in a publicly accessible website, such as ClinicalTrials.gov.

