7.1 Inclusion Criteria

Subject eligibility is determined according to the following criteria prior to entry into the study:

1. In the opinion of the investigator, the subject is capable of understanding and complying with protocol requirements.
2. The subject signs and dates a written, informed consent form and any required privacy authorization prior to the initiation of any study procedures including requesting that a subject fast for any laboratory evaluations.
3. The subject is a healthy male or female.
4. The subject is aged 18 to 55 years, inclusive, at the time of informed consent and first study drug dose.
5. The subject has an eGFR ≥ 90 mL/min.
6. The subject weighs at least 50 kg and has a body mass index (BMI) from 18.5 to 30.0 kg/m², inclusive at Screening.
7. A male subject who is nonsterilized* and sexually active with a female partner of childbearing potential* agrees to use barrier method of contraception (eg, condom with or without spermicide)* from signing of informed consent throughout the duration of the study and for 35 days after last dose. A female subject of childbearing potential* who is sexually active with a nonsterilized* male partner agrees to use an effective method of contraception* from signing of informed consent and throughout the duration of the study and for 35 days after last dose.

* Definitions and effective methods of contraception are defined in Section 9.1.9 and reporting responsibilities are defined in Section 9.1.10.

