9.1.1 Informed Consent Procedure

The requirements of the informed consent are described in Section [15.2](#).

Informed consent must be obtained prior to the subject entering into the study, and before any protocol-directed procedures are performed, including requesting that a subject fast for laboratory evaluations.

A unique subject identification number (subject number) will be assigned to each subject at the time that informed consent is obtained; this subject number will be used throughout the study.

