9.1.9 Contraception and Pregnancy Avoidance Procedure

From signing of informed consent, throughout the duration of the study, and for 35 days after last dose of study medication, female subjects of childbearing potential* who are sexually active with a nonsterilized male partner** must use an effective or highly effective method of contraception from the list below.

In addition, they must be advised not to donate ova during this period.

The following definitions apply for contraception and pregnancy avoidance procedures.

* A woman is considered a woman of childbearing potential, ie, fertile, following menarche and until becoming postmenopausal unless permanently sterile. Permanent sterilization methods include hysterectomy, and bilateral oophorectomy. A postmenopausal state is defined as no menses for 12 months without an alternative medical cause. A high follicle stimulating hormone (FSH) level in the postmenopausal range (FSH >40 IU/L) may be used to confirm a postmenopausal state in younger women (eg, those <45 years old) or women who are not using hormonal contraception or hormonal replacement therapy. However, in the absence of 12 months of amenorrhea, a single FSH measurement is insufficient.

** Sterilized males should be at least 1 year post-bilateral vasectomy and have confirmed that they have obtained documentation of the absence of sperm in the ejaculate or have had bilateral orchidectomy.

Highly effective methods of contraception are defined as those, alone or in combination, that result in a low failure rate (ie, less than a 1% failure rate per year when used consistently and correctly). In this study, where medications and devices containing hormones are excluded, highly effective methods of contraception are:

Non-Hormonal Methods

- Copper T PLUS condom or spermicide.
- Bilateral Tubal Occlusion.

- Vasectomized partner (provided that partner is the sole sexual partner of the trial participant and that the vasectomized partner has received medical assessment of the surgical success.

Genotoxicity/teratogenicity/embryotoxicity is unlikely to be caused by the investigational drugs. Therefore, an effective method of contraception where there may be a higher than 1% failure rate can be used. An effective method of contraception is:

Barrier methods:

- Double-barrier method (contraceptive sponge, diaphragm or cervical cap with spermicidal jellies or creams PLUS male condom).

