Female subjects must discontinue any use of hormonal contraceptives (if applicable), at least 2 months before the start (Day-1) of the trial.

Subjects will be provided with information on effective and highly effective methods of contraception as part of the subject informed consent process and will be asked to sign a consent form stating that they understand the requirements for avoidance of pregnancy and donation of ova during the course of the study.

During the course of the study, regular urine human chorionic gonadotropin (hCG) pregnancy tests will be performed only for women of childbearing potential and subjects will receive continued guidance with respect to the avoidance of pregnancy as part of the study procedures ([Appendix A](#)). In addition to a negative urine hCG pregnancy test at Screening, subjects also must have a negative urine hCG pregnancy test at Check-in (Day-1 of each Period) prior to receiving any dose of study medication.

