9.3.1 Screening

Subjects will be screened within 28 days prior to randomization. Screening may consist of 1 or more visits. Subjects will sign an informed consent form at the first visit and return to the clinic in a fasted state for safety laboratory testing at the second visit. Subjects will be screened in accordance with predefined inclusion and exclusion criteria as described in Section 7.0. A screen failure rate of approximately 50% is anticipated. Therefore, an estimated 144 subjects will be screened in order to enroll 72 subjects. See Section 9.1.14 for procedures for documenting screening failures.

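### Appendix C item 24 tells women they must use highly effective contraception, while inclusion 7 and Section 9.1.9 accept a lower tier

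*Protocol*

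**What the plan says.** Four places in the protocol bear on the standard for female subjects.

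- **Appendix C, item 24** (information to be given to each subject): sexually active women of childbearing potential "who are sexually active must use highly effective contraception (as defined in the informed consent) from Screening and throughout the duration of the study". Item 24 extends this to a point 35 days past the final dose.
- **Section 7.1, inclusion 7**: a woman of childbearing potential who is sexually active with a nonsterilized "male partner agrees to use an effective method of contraception", from consent until 35 days after the last dose.
- **Section 9.1.9, standard and tiers**: such women "must use an effective or highly effective method of contraception from the list below". The section defines highly effective as a failure rate under 1% per year. It then says the study drugs are unlikely to be genotoxic, teratogenic or embryotoxic, and continues: "Therefore, an effective method of contraception where there may be a higher than 1% failure rate can be used". The only method listed in that lower tier is double barrier.
- **Section 9.1.9, consent process**: subjects are to be informed about both tiers as part of consent.

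On hormonal methods, Section 9.1.9 says: "Female subjects must discontinue any use of hormonal contraceptives (if applicable), at least 2 months before the start (Day-1) of the trial". Table 7.a in Section 7.3 gives the same restriction as a 60-day look-back from Day -1.

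**The concern.** The consent content and the eligibility text state different requirements for the same women over the same period. If the consent form is written from item 24, a woman using double barrier will have been accepted under inclusion 7 and then told that she must use something more reliable. If it is written from Section 9.1.9, it will not contain what Appendix C says it must.

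What is at stake is the clarity of consent and a consistent instruction on pregnancy avoidance. Site staff need one answer to give when a subject asks whether her method is acceptable, and the current text gives two.

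**Working it through.** **1. The standards side by side**

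- Appendix C item 24: highly effective only.
- Inclusion 7: effective.
- Section 9.1.9: effective or highly effective.

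**2. Can the terms be read as the same thing?** No. Section 9.1.9 separates them by failure rate (under 1% per year against possibly above 1%) and lists different methods under each. With hormonal products excluded, the highly effective list is a copper T with condom or spermicide, bilateral tubal occlusion, or a vasectomized partner. Double barrier stands alone in the lower tier.

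**3. Test cases**

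- Copper T plus condom: meets inclusion 7, Section 9.1.9 and item 24.
- Double barrier: meets inclusion 7 and Section 9.1.9, but not item 24.

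**4. Period over which the mismatch applies.** Item 24 starts at Screening and inclusion 7 at the signing of consent. Consent is signed at the first Screening visit (Section 9.3.1), so the two starts coincide. There is no Day 0, so Day -k is k days before Day 1.

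- Earliest consent, Day -28, to Period 1 Day 1: 28 days.
- Period 1 Day 1 to Period 4 Day 1: 3 × 7 = 21 days.
- After the last dose: 35 days.
- Longest span with 7-day intervals: 28 + 21 + 35 = 84 days. With consent on Day -2: 2 + 21 + 35 = 58 days.

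The Day -28 start agrees with the plan's stated total duration of approximately 66 days. Screening is 28 days, Period 1 Day 1 to Period 4 Day 4 is 3 × 7 + 3 = 24 days, and the call 14 days after study exit (Appendix A) gives 28 + 24 + 14 = 66. Timing the call from the last dose, as the body text does, gives 28 + 21 + 14 = 63.

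**5. Amendment history.** Appendix F, Change 2, lists item 24 among the places edited for the 35-day period. The item was therefore open for revision in Amendment 02, and the tier mismatch remains in the current text.

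**6. The hormonal stop date**

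- 60 days before Day -1 is 60 + 1 = 61 days before Day 1.
- Earliest consent is 28 days before Day 1 ("Subjects will be screened within 28 days prior to randomization").
- The stop therefore falls 61 − 28 = 33 days before the earliest consent. Reading 2 months as 59 to 62 days gives 32 to 35 days.
- The difference between 2 months and 60 days is thus −1 to +2 days, depending on the calendar.

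**The case against.** The case for leaving the text alone has four parts.

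- **Item 24 is not an entry criterion.** Section 9.1.15 makes eligibility depend on the inclusion and exclusion criteria, and inclusion 7 and Section 9.1.9 agree in accepting an effective method. This stands. A reader might infer that different sites will enrol different women, but the documents do not support that: item 24 does not decide who enters, and there is one site.
- **Item 24 defers to the definition in the consent form.** The form was not available, so nobody can say what subjects were actually told or that anyone breaches what she signs. That limit stands, but the deferral does not remove the conflict. A form that follows the tiers in Section 9.1.9 leaves double barrier short of item 24, and a form that calls double barrier highly effective contradicts Section 9.1.9.
- **Section 9.1.9 says both tiers will be explained at consent.** This suggests that the intention was to allow both. It also means item 24, which names only the higher tier, does not describe that process.
- **Item 24 looks like unadapted template text.** It also offers unblinded treatment information in an open-label study. That explains the mismatch but does not cure it.

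A stronger reading is tempting on hormonal methods. Because the stop date precedes any possible consent, a reader might infer that the rule can be met only by changing a candidate's contraception before consent, and that this raises pregnancy risk. The dates are right; the inference is not. Table 7.a words the rule as something already done, and exclusion 10 excludes anyone who used a listed product within its window. Other look-backs, such as the 90-day rule for the study drugs, also predate consent. A current user is simply ineligible, and a woman who had already stopped qualifies. Nothing directs staff to stop anyone's method early, and Section 9.1.1 points the other way: "Informed consent must be obtained prior to the subject entering into the study, and before any protocol-directed procedures are performed". Nor is the added pregnancy risk shown. Exclusion 12 rules out women with unprotected sex in the 30 days before dosing, and urine pregnancy tests must be negative at Screening and at every Check-in.

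**Conclusion.** The contradiction over the standard holds in the current text. Appendix C item 24 requires the higher tier; inclusion 7 and Section 9.1.9 accept the lower one. It concerns women relying on double barrier, for 58 to 84 days each if doses are exactly 7 days apart. The documents do not say how many women will be enrolled or which methods they will use, so no count is possible. The conclusion rests on Section 9.1.9's own definitions of the tiers and on Appendix C governing the content of the consent form. It does not rest on the form itself, which was not seen.

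The effect is on consent and on the instruction given to subjects. No endpoint, analysis or power statement changes.

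On hormonal contraceptives, only a minor wording difference remains: an imperative with a 2-month limit in Section 9.1.9 against a 60-day look-back in Table 7.a. It is not a contradiction with the consent timing.

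**What to change.** Reconcile Appendix C item 24, inclusion 7 and Section 9.1.9 to one stated contraception standard for female subjects, and carry the same wording into the consent form. Which standard that should be is for the sponsor and the responsible clinicians; no view is given here.

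In the same amendment, reconcile the hormonal-contraceptive sentence in Section 9.1.9 with Table 7.a so that both state the restriction in the same form and the same unit of time.

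The cost is a protocol wording amendment and, if the consent form has to change, its re-approval by the ethics committee. No procedure, visit or analysis is added.
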